A comparison of Mepitel Ag vs antibiotic ointment when used with a soft cast technique for the treatment of pediatric hand and foot burns, a prospective study

Protocol #: 15-1828

April 8, 2016

COMIRB Protocol

COLORADO MULTIPLE INSTITUTIONAL REVIEWBOARD
[name] [contact] [contact]

Protocol #: 15-1828

Project Title: A comparison of Mepitel Ag vs antibiotic ointment when used with a soft cast technique for the treatment of pediatric hand and foot burns, a prospective study

Principal Investigator: [name], MD

Version Date: 3/30/16

- I. **Hypotheses:** Mepitel Ag in combination with the soft cast technique improves wound healing in pediatric partial to deep partial thickness hand and foot burns by decreasing the length of healing time, decreasing the risk of yeast infection, and decreasing pain associated with multiple dressing changes.
- II. **Specific Aims:**
 - 1) To examine the efficacy of Mepitel Ag for use in pediatric partial to deep partial thickness hand and foot burns.
 - 2) To evaluate Mepitel Ag to triple antibiotic ointment when used in combination with a soft cast technique comparing healing time, yeast infection rates and pain levels at time of dressing change.

II. Background and Significance:

There is currently no gold standard dressing when it comes to treating hand or foot burns, specifically in the pediatric population. Our institution currently utilizes a soft cast technique (SCT) on all of our hand and foot burns. The SCT provides optimal positioning of the wounded hand or foot, allows for a moist wound environment, and offers protection of the injured extremity as the wound heals. Our current SCT uses triple antibiotic ointment (TAO) impregnated Adaptic gauze, kling or kerlex, cast padding, gypsoma plaster, soft cast material, and coban. This dressing is applied two to three times during the first 2 weeks post injury. To reduce the risk of the development of yeast overgrowth, the underlying dressing is changed to nystatin impregnated Adaptic gauze, kling or kerlex, cast padding, gypsoma plaster, soft cast material, and coban for the remainder of treatment time or until OR is indicated for surgical debridement and grafting of wounds..

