This is due to the fact that “soft silicone dressing have been shown to prevent trauma to the wound bed and periwound skin and have been described as ‘atraumatic’”.¹⁴ Other benefits of soft silicone dressings include the ability to conform to anatomical contours, a reduction in scar development, and reduced overall cost secondary to improved wound healing and need for less frequent dressing changes.¹⁴

Mepitel Ag, a hybrid type soft silicone dressing impregnated with a silver compound was recently approved for use in partial thickness burns and partial and full thickness grafts.¹⁵ This combination of soft silicone and silver provides a relatively pain free dressing with broad spectrum antibiotic coverage. The aim of this study is to demonstrate that Mepitel Ag in combination with a soft cast technique is a superior alternative to antibiotic ointment impregnated gauze and soft cast for the treatment of pediatric hand and foot burns due to decreased healing time, decreased patient pain and lower yeast infection rates.

IV. Research Methods

A. Outcome Measure(s):

Primary outcomes utilized in this study include overall wound outcome, measured in length of days to re-epithelialization or need for surgical intervention, clinical assessment and wound progression photographs. Secondary outcomes include number of patients requiring surgical debridement, presence of infection based on odor, rash, deep red appearance or puritis. These wounds will not be cultured, patient pain level with dressing change based on the FLACC (Face, Legs, Activity, Cry, Consolability) scale, parents perceived level of pain, pain level at home based on family reported pain and pain medication use. We will also assess cost effectiveness of dressings including the number of clinic visits, number of soft casts, and the cost and amount of dressings used over the course of treatment.

B. Description of Population to be Enrolled:

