Patients to be included in this study will be all Children's Hospital Colorado burn patients between the ages of 31 days and 18 years with newly diagnosed partial to deep partial or full thickness hand or foot burns, including bilateral or unilateral injury. Each injured extremity will serve as a separate data point. Exclusions include age > 18 years at start of study, silver allergy, silicone allergy, electrical or chemical burn, past medical history of immunodeficiency disorders such as diabetes mellitus, AIDs, or HIV, pregnant women, prisoners children under the protection of the department of human services, and the decisionally challenged.

C. Study Design and Research Methods

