New burn clinic patients identified with a partial to deep partial or full thickness hand or foot burn will be randomized into either the Mepitel Ag group or the control group on their first clinic visit based on burn wound severity and age using RedCap. The randomization scheme in RedCap will be independently created by a statistician. Parental consent and or patient assent will be obtained prior to initial dressing. Burn severity will be clinically determined by one provider and one burn nurse during initial exam based on a 10 point burn severity classification scale in regards to the following parameters: 1) Superficial first degree- wound appears pink or red, involves epidermis only, no blisters present, dry; 2) Second degree, superficial partial thickness- burn involves epidermis + dermis, red or bright pink in color with blisters and or swelling, blanches, moist appearing; 3) Second degree, majority superficial partial thickness, minority superficial- burn involves majority ($\geq 66\%$) superficial partial thickness, epidermis + dermis, red or bright pink in color with blisters and or swelling, blanches, moist appearing, minority ($\sim 33\%$ or less) superficial first degree with areas of redness but no blistering; 4) Second degree, majority partial thickness, minority deep partial thickness- majority of burn ($\geq 66\%$) epidermis + dermis, red or bright pink in color, moist, less than half of burn ($\sim 33\%$ or less) is deep with pale pink-white areas, may or may not have a marbled or mosaic appearance; 5) Second degree, deep partial thickness- involves epidermis + dermis, pale pink to white in color, may have thin white moist eschar, may or may not have a marbled or mosaic type appearance, moist; 6) Second degree, majority deep partial thickness, minority superficial partial thickness- minority of burn ($\sim 33\%$ or less) involves epidermis + dermis, red or bright pink in color, moist, majority ($\geq 66\%$) of burn is deep with pale pink-white areas having a marbled or mosaic appearance, may or may not have thin white moist eschar, skin buds may or may not be present; 7) Second degree, deep partial thickness with areas of full thickness- majority of burn ($\geq 66\%$) involves epidermis + dermis, pale pink to white in color, may have thin white moist eschar, may or may not have a marbled or mosaic type appearance, moist, skin buds may or may not be present, minority of burn ($\sim 33\%$ or less) demonstrates thin to thick area of eschar white, brown or black in color, may need skin graft to heal; 8) Third degree full thickness with minority partial thickness- majority of burn ($\geq 66\%$) involves entire dermis + epidermis, thin to thick eschar that is white, brown or black in color, dry appearing, minority of burn ($\sim 33\%$ or less) is pink or red and moist, with blisters and or swelling, blanches; 9) Third degree full thickness- involves entire dermis + epidermis, thin to thick eschar that is white,

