
brown or black in color, dry appearing; 10) Fourth degree- third degree + muscle and or bone involvement. The provider and burn nurse will each give the patient a number and the severity will be determined based on the average of the 2 numbers. Any patient given a number 2, 3 or 4, will be placed into the "partial thickness" category, any patient given a 5, 6, or 7 will be placed into the "deep partial thickness" category, and lastly, any patient given an 8 or 9 will be placed into the "full thickness" category for burn severity.

Patients will be randomized into one of two groups, Mepitel Ag or standard TAO, using RedCap and based on a random clinical trial excel spread sheet balanced by burn severity. A statistician will provide a randomization scheme for investigators to follow. Photographs will be taken prior to dressing application at the initial visit and each subsequent visit. ~~Patient wounds will be dressed in either Mepitel Ag, kling or kerlex, cast padding, gypsoma plaster, soft cast material and coban for up to 21 days or until complete re-epithelialization of the wound occurs or unless surgery is indicated; the control, standard dressing of Triple Antibiotic Ointment impregnated adaptic gauze, kling or kerlex, cast padding, gypsoma plaster, soft cast material and coban for 10-14 days, or Nystatin impregnated adaptic, kling or kerlex, cast padding, gypsoma plaster, soft cast material and coban for 8-21 days or until complete re-epithelialization of the wound occurs or surgery is indicated. The SCT is applied by Occupational and Physical trained in casting and positioning. The soft cast provides optimal positioning while eliminating friction on the burn area. Dressing changes will occur every 3-10 days and will be determined by the provider, based on burn wound severity. Upon each return clinic visit, the patient will have their wound severity assessed by the following scoring system: 1=0% healed, 2=20% healed; 3=40% healed; 4=60% healed; 5=80% healed; 6=100% healed. This will be established by provider and burn nurse examination of the wound. This will be recorded in RedCap:_____~~

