A member of the nursing team will also complete a questionnaire at each follow up visit to indicate pain level with dressing change based on the FLACC scale, parents perceived level of pain during dressing change, parental reported pain level at home, use of home pain medications, type of home pain medication- narcotic vs non-narcotic, clinical assessment of yeast rash including odor, visible rash, use of fluconazole, ease of dressing application, and amount and type of product used in dressing change.

D. Description, Risks and Justification of Procedures and Data Collection Tools:

A photography release will be distributed and signed by parent at initial visit.

Anursing questionnaire will be completed by nursing staff at each follow up appointment.

Local wound care including cleansing, wound measurement and dressing change will be performed by burn team including nursing staff and occupational and physical therapists. Although punch biopsy with histological analysis is considered the 'gold standard' in assessing burn wound depth, it is invasive and time consuming.¹⁸ Clinical assessment remains the most frequent and rapid method.¹⁸ Due to the time sensitive nature of the proposed trial and in order to avoid delaying wound care and initial dressing application, a 10 point clinical assessment scale has been created, as listed above for use in determining initial burn wound severity. Patient wound depth will be clinically determined by the average of the scores from the provider and the burn nurse.

The wound will also be assessed by the provider and nurse on subsequent visits using the following scoring tool: 1=0% healed, 2=20% healed; 3=40% healed; 4=60% healed; 5=80% healed; 6=100% healed. This will be established by provider and burn nurse examination of the wound. This will be recorded in RedCap.

The overall risk for this study is minimal, with no foreseen adverse reactions. The risk of a silver allergy or adverse reaction to silicone is very rare.

E. Potential Scientific Problems:

Limitations to the proposed study design include varying diagnostic opinions between provider and burn nurse for the determination of superficial vs deep partial thickness burn wounds based on clinical assessment, provider or nurse bias based on dressing preference, and possible uneven trial groups.

F. Data Analysis Plan:

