Analysis Plan: Demographic and clinical characteristics will be summarized and compared between the two treatment groups using chi-squared and two-sample t-tests for categorical and continuous data, respectively. For analysis of the primary outcome, time to wound healing, we will use Kaplan-Meier curves, the log-rank test and a Cox proportional hazards model to determine the difference in days to re-epithelialization between the TAO and Mepitel Ag soft cast methods. Patients that require surgical intervention will be censored at the time of surgery. Logistic regression will be used to analyze the secondary outcomes, need for surgical debridement and occurrence of yeast infection. Pain level outcomes and pain medication use will be compared using two-sample t-tests and chi-squared tests. Cost effectiveness outcomes will also be analyzed.

1. Sample size: A statistical power analysis was performed to estimate power, based on results reported in A Soft casting Technique to Manage Pediatric Hand Burns: Less Pain, Greater Gain.²² Considering the simplest between group comparison and assuming a standard deviation of 0.3, alpha of 0.05 and 50 subjects per group there is over 90% power to detect a difference of 2 days between the treatment groups. Thus, we expect that our proposed sample size of 100 burns will be adequate for the main objective of this study.

G. Summarize Knowledge to be Gained:

To demonstrate that Mepitel Ag in combination with a soft cast technique improves wound healing in pediatric partial to deep partial thickness hand and foot burns by decreasing the length of healing time, decreasing the risk of yeast infection, and decreasing pain associated with dressing changes.

H. References:

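### The pain-score comparison ignores age and burn severity and has no pre-allocation pain score, so it is valid but possibly less precise than it could be

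*Combined protocol and SAP*

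**What the plan says.** The Hypotheses section includes "decreasing pain associated with multiple dressing changes" as the third of three expected benefits. Section IV.A places pain among the secondary outcomes, measured as "patient pain level with dressing change based on the FLACC (Face, Legs, Activity, Cry, Consolability) scale, parents perceived level of pain", together with pain and medication use at home.

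Timing is stated twice. Section IV.C: "A member of the nursing team will also complete a questionnaire at each follow up visit to indicate pain level with dressing change". Section IV.D says again that the "questionnaire will be completed by nursing staff at each follow up appointment". For the first visit the protocol describes a severity score from a provider and a burn nurse, a photography release and photographs ("Photographs will be taken prior to dressing application at the initial visit and each subsequent visit"). It mentions no pain score there.

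Randomization takes place "on their first clinic visit based on burn wound severity and age using RedCap". A later paragraph of IV.C mentions balance by severity only. Eligible children are "between the ages of 31 days and 18 years" (IV.B), and burns fall into three severity categories (IV.C).

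On analysis, IV.F says: "Pain level outcomes and pain medication use will be compared using two-sample t-tests and chi-squared tests". It names no covariate and no visit for pain. IV.B makes each injured extremity its own data point.

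**The concern.** Every pain score is taken after allocation and after the assigned dressing has been worn. Children from infancy to 18 years, with burns of three severity categories, can be expected to differ in distress and pain for reasons unrelated to the dressing. The documents do not quantify this, so it is an assumption, but a plausible one. A two-sample t-test leaves all such variation in the error term.

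What is at stake is precision on one of the three claims the trial wants to make. Two sources of precision go unused. Age and severity are in hand before allocation, and IV.C names both as the basis for it, but the pain test uses neither. A pain score at the initial wound examination is not planned, and it cannot be recovered once a child has been dressed.

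**Working it through.** **The plan's own figure.** IV.F gives power for healing time only: 50 per group, SD 0.3, difference 2 days, alpha 0.05. The standard error is 0.3 × √(2/50) = 0.06 days and 2/0.06 = 33.3, so power is effectively 100%. The statement of over 90% is reproduced as a lower bound. It says nothing about pain, for which the plan gives no SD, target difference or power. Whether 0.3 is a sensible SD for healing days is a separate question.

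**Inputs for pain.** From IV.F: 50 per group and alpha 0.05 (two-sided assumed). Differences are in units of the pain-score SD. Assumed, because the documents give no value: r, the correlation of follow-up pain with the covariate, or the multiple correlation with several covariates together. A difference of 0.5 SD is used for illustration only.

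**Formulas.** Unadjusted, the smallest difference detectable with 80% power is (1.960 + 0.842) × √(2/50) = 2.802 × 0.2 = 0.56 SD. Adjustment multiplies residual variance by 1 − r², and so multiplies the detectable difference by √(1 − r²). Power for 0.5 SD is Φ(0.5 / (0.2 × √(1 − r²)) − 1.960).

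| Assumed r | Variance factor 1 − r² | Reduction | Detectable difference, 80% power (SD) | Power for 0.5 SD |
|---|---|---|---|---|
| 0 (t-test) | 1.00 | 0% | 0.560 | 70.5% |
| 0.1 | 0.99 | 1% | 0.558 | 71.0% |
| 0.2 | 0.96 | 4% | 0.549 | 72.3% |
| 0.3 | 0.91 | 9% | 0.535 | 74.6% |
| 0.5 | 0.75 | 25% | 0.485 | 82.3% |

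**Two cautions.**

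- The table ignores the cost of estimating the covariate coefficients. Age, three severity categories (two coefficients) and a baseline score use four of the 98 residual degrees of freedom (100 − 2). That costs roughly 98/94 = 1.04 in variance. Covariates that together explain less than about 4% of the variance would therefore give no net gain.
- The table treats the 50 per group as independent children with one score each. The plan counts extremities and scores pain at every follow-up visit, so 50 is an upper bound on independent children per group. The table shows the scale of the gain and does not forecast the trial's power.

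**The case against.** The strongest reply is that nothing here is wrong. Allocation is randomized, so an unadjusted comparison of follow-up pain is unbiased with respect to initial pain, and the test's error rate already allows for chance imbalance. Pain is secondary and no power is claimed for it. This stands. A reader might infer that the missing baseline score biases the pain result or makes it uninterpretable. The documents do not support that reading, because randomization precedes every score.

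A second reply concerns the size of the gain. The outcome is pain when a dressing is changed, and the mechanism in the Background is gauze that dries and sticks. At the first visit no study dressing has been removed, so a score then reflects a different stimulus and r may be below 0.3. This also stands. A reader might take r = 0.5 from the table and conclude that the plan forgoes the equivalent of a third more children (1/0.75 = 1.33). The documents give no correlation to support that. With repeated visits and two extremities per child, the equivalence does not carry over directly.

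Third, basing allocation on severity and age limits gross imbalance on those factors, and IV.F already compares clinical characteristics between the arms. So it would go too far to say that unequal groups could not be noticed at all. Only unequal initial pain would go unseen. Balance by design does not remove the precision argument: variation due to age and severity within each arm stays in the error term unless the model includes them.

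Finally, time is short at the first visit. IV.D stresses not delaying wound care, and IV.C requires consent only before the initial dressing. This is a real but small cost.

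**Conclusion.** The point holds as a minor improvement in efficiency. Pain is scored only after allocation, the planned t-test uses no covariate, and two prognostic factors known at randomization are left out. The comparison is not biased by this; it may be less precise than the same trial could deliver.

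The size is undetermined. Residual variance falls by 1% to 25% for r between 0.1 and 0.5, less the small cost of estimating the coefficients, and r is an assumption throughout. At the low end the benefit is effectively nil. At r = 0.5, power for an illustrative 0.5 SD difference would rise from 70.5% to 82.3%, given 50 independent children per group. The case for adjusting for age and severity comes first, since it needs no new data. The first-visit score is a cheap addition whose value depends on how well it predicts later dressing-change pain.

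The plan also leaves open which visit enters the pain test and how two extremities of one child are counted. Any replacement analysis must settle both, or it will be as loosely specified as the t-test.

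**What to change.** **In IV.F**, replace the t-test for pain scores with a linear model of follow-up pain on treatment arm, adjusted for age and burn severity category. State either one visit, for example the first dressing change, or a repeated-measures model over all follow-up visits. In either case allow for clustering by child.

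**In IV.C and IV.D**, add one FLACC score and one parent rating at the initial wound examination, after consent and before allocation is revealed, and include that score as a covariate in the model. The examination is a natural moment: allocation depends on severity, so the burn nurse must already score the wound before it. Only the pain items of the questionnaire are needed, as the rest concerns follow-up. State in advance how a missing baseline score is handled.

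**Cost.** The age and severity adjustment needs only text. The extra score takes a few minutes per child, moves consent ahead of the examination, and needs a simple missing-data rule. It helps only children enrolled after the change.

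### The primary Cox model names no covariates; prespecify the randomisation factors, pre-dressing wound size and hand versus foot

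*Combined protocol and SAP*

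**What the plan says.** The combined protocol and SAP gives the primary analysis in one sentence of IV.F: "we will use Kaplan-Meier curves, the log-rank test and a Cox proportional hazards model" for days to re-epithelialization. Surgery censors. No covariate or stratification factor is named, and none is ruled out. IV.F also plans to compare baseline characteristics between groups with chi-squared and t-tests.

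On the candidate covariates:

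- **Site.** IV.B admits "hand or foot burns, including bilateral or unilateral injury", so hand or foot is known before allocation. Each affected limb counts as its own observation.
- **Wound size.** IV.D states: "Local wound care including cleansing, wound measurement and dressing change will be performed by burn team". It gives no timing, method or unit, and does not say that the result is kept. The follow-up item that IV.D says goes into RedCap is the six-level percent-healed score.
- **Severity and age.** IV.C bases the allocation on burn severity and age in one place, and on severity alone in another. Neither factor appears in the analysis.

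The sample size rests on an unadjusted calculation, introduced by the words "Considering the simplest between group comparison". Its inputs are 50 per group, an SD of 0.3 with no unit given, and a 5% significance level. From these IV.F concludes that "there is over 90% power to detect a difference of 2 days between the treatment groups".

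**The concern.** A Cox model with treatment as its only term adds almost nothing to the log-rank test as a test of the primary comparison. The population runs from 31 days to 18 years, mixes hands with feet, and spans partial to full thickness. If size or site predicts healing, leaving it out pulls the hazard ratio towards 1 and costs power. In a trial of 100 burns, a chance imbalance in such a factor could also create or hide part of a 2-day effect.

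Testing baseline characteristics between groups can show an imbalance but does not correct it. With no covariates fixed in advance, it also invites a choice of adjustment after the data are seen. Omitting the randomisation factors is a gap of the same kind: the design balances on severity (and perhaps age), and the analysis does not use them.

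**Working it through.** **1. The plan's own power figure.** Inputs from IV.F: difference 2 days, SD 0.3 (taken as days), 50 per group, alpha 0.05 (taken as two-sided).

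SE = 0.3 × √(2/50) = 0.06, and 2/0.06 = 33.3, so power is about 100%. The claim of over 90% is true but uninformative: n per group for 90% is 2 × (1.960 + 1.282)² × 0.3²/2² = 0.47, rounded up to 1. The SD that gives exactly 90% with 50 per group is 2/(0.2 × 3.242) = 3.08 days. On the plan's inputs adjustment can add nothing, so any illustration needs an assumed spread.

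**2. Illustration with log-normal healing.** Assumed: control mean 14 days, SD 5, 2-day effect, 50 independent burns per arm, end of follow-up at 35 days. Here r is the correlation of log wound size with log healing time. Simulated Cox power, as ranges over repeated simulations where there were several:

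| r | Unadjusted | Adjusted | Gain (points) |
|---|---|---|---|
| 0 | 51% | 51–52% | about 0 |
| 0.1 | 50.3% | 51.8% | 1.5 |
| 0.2 | 51.5% | 54.0% | 2.5 |
| 0.3 | 52–53% | 56–58% | roughly 5 |
| 0.5 | 51–53% | 65–67% | roughly 14 |

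With 3,000 runs the Monte Carlo standard error of one entry is √(0.5 × 0.5/3000) = 0.9 points.

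These gains are gross. The adjusted test's type I error was about 7% at r = 0.3 and 0.5, against a nominal 5%. After recalibration to 5%, the gains were about 2 points at 0.3 and 10 at 0.5.

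**3. Mechanism.** At r = 0.5 the standard error of the log hazard ratio rose from 0.206 to 0.213, while the estimate moved from 0.42 to 0.52. The ratio of estimate to standard error goes from 0.42/0.206 = 2.04 to 0.52/0.213 = 2.44. Power rises because attenuation falls.

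**4. Check where the Cox model is correctly specified.** Assumed: Weibull times, about 5% censored (about 95 healing events), 40% foot burns, conditional hazard ratio 1.8, 4,000 runs per row. Coefficients are log hazard ratios per SD of log size and for foot.

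| Size, foot coefficients | Unadjusted | Adjusted |
|---|---|---|
| 0, 0 | 80% | 80% |
| −0.25, −0.2 | 75% | 79% |
| −0.5, −0.3 | 66% | 79% |
| −0.8, −0.4 | 53% | 79% |

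The Schoenfeld formula gives Φ(√(95/4) × ln 1.8 − 1.96) = Φ(2.86 − 1.96) = 82%, close to the first row. In the third row the log hazard ratio is 0.50 unadjusted and 0.61 adjusted (true value ln 1.8 = 0.59), and the standard error goes from 0.213 to 0.220. The mechanism is the same as in step 3.

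**5. Chance imbalance.** The standard error of the between-arm difference in standardised log size is √(1/50 + 1/50) = 0.2 SD. A two-standard-error imbalance is 0.4 SD. At r = 0.5 and SD 5 days it shifts apparent healing time by about 0.4 × 0.5 × 5 = 1.0 day, half the target difference.

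**The case against.** The strongest reply is that the plan is silent on covariates rather than opposed to them, that the documents do not show how strongly size or site predicts healing, and that no baseline wound size is shown to be collected. All three points stand, and they rule out several stronger readings.

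- A reader might infer that wound size is already measured and stored at every visit and then thrown away. IV.D only lists measurement as a wound-care task. Size at later visits would in any case be unusable as a covariate, because treatment affects it.
- A reader might call the gain free precision. In a Cox model the standard error does not shrink, and the estimate becomes conditional on the covariates. Sample-size equivalents from 1/(1 − r²), such as 1.10 at r = 0.3 and 1.33 at r = 0.5, belong to linear models. The log-rank test gains nothing unless it is stratified.
- A reader might take the remark in IV.E that the trial groups may be uneven as an admission about wound size. It does not mention size, and may refer to group numbers.
- The title of the power source refers to hand burns, but that says nothing about whether site predicts healing.

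It is also fair to object that adjusting for size and site alone would miss the randomisation factors and children with two injured limbs, and that a given area means something different on an infant's hand and an adolescent's. The fix therefore covers severity, age and clustering.

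What survives is that a non-prognostic covariate costs almost nothing (51% against 51–52%, and 80% against 80%), so prespecifying these terms has little downside.

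**Conclusion.** The point holds as a worthwhile improvement, not as an error that invalidates the trial. The primary Cox model is unspecified beyond its name, and prespecified adjustment would usually raise power and protect against chance imbalance.

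The size cannot be derived from the documents. Under the log-normal assumptions it is about 0 points at r = 0, roughly 5 at r = 0.3 and 14 at r = 0.5, before allowing for the type I error of about 7%; the net gain is smaller. At the plan's SD of 0.3 the gain is nil, but that SD would justify one burn per group and so cannot show that adjustment is unnecessary.

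The illustrations assume independent burns and model-based standard errors. Two limbs from one child are likely to be positively correlated, which would lower the effective sample size. The clustered variance recommended below was not part of the simulations, so they do not show whether it removes the type I error inflation.

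**What to change.** 1. Add a RedCap field for wound size, measured at the first visit before the first dressing, with method and unit stated. Use only this value as a covariate.
2. In IV.F, name as primary a Cox model for days to re-epithelialization with treatment, burn severity category, age if it is used in the allocation, log baseline wound size, and hand versus foot, fitted whatever the baseline balance. Reconcile the two statements of the allocation factors in IV.C, so that the age term is settled.
3. Use a robust variance clustered by child, because each limb is a separate observation.
4. Report the unadjusted log-rank and Cox results as a sensitivity analysis, and state that the primary hazard ratio is conditional on the covariates.

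The cost is one data field, a measurement at a defined time, and a few sentences in IV.F. The three severity categories of IV.C take two terms, and age (as one term), size and site take three more. With treatment that makes six terms, or about 95/6 = 16 events per term if some 95 burns heal (an assumption; the documents give no expected number of events). The main price is the change to a conditional hazard ratio.
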